#### **3.6.3 Full Analysis Set**

The Full Analysis Set (FAS) will consist of all subjects in the ES who received at least 1 dose of study medication in PA0009 and have a valid measurement for at least 1 efficacy variable after PA0009 EV.

Secondary and other efficacy variables will be summarized for the FAS. Immunological variables will also be summarized on the FAS where specified in [Section 9.2](#).

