13.1 Definition of analysis sets

The Enrolled Set (ES) will consist of all subjects who have given informed consent for PA0009.

The Safety Set (SS) will consist of all subjects who receive at least 1 dose of the IMP in PA0009.

The Full Analysis Set (FAS) will consist of all enrolled subjects who receive at least 1 dose of the IMP and have a valid measurement for at least 1 efficacy variable after PA0009 entry visit.

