13.8 Handling of dropouts or missing data

Missing binary efficacy variables will be imputed using nonresponder imputation (NRI). In NRI, each subject with missing data or who has prematurely finished the study will be counted as a nonresponder.

For missing continuous efficacy variables, a multiple imputation (MI) approach will be used. In MI, the missing value is replaced by a set of plausible values, where each value is a Bayesian draw from the conditional distribution of the missing data given the observed data.

Non-monotone missing data (ie, intermittent missing data) will be imputed several times with the Markov Chain Monte Carlo (MCMC) method and monotone missing data will be imputed using a monotone regression model. Each set of imputed data will then be summarized and the summaries will be combined into a single inference (Carpenter and Kenward, 2013).

Safety data will not be imputed.

As a sensitivity analysis, the ACR, PASI, LDI, MASES, and MDA efficacy variables will be analyzed based on observed data in addition to a sensitivity analysis based on multiple imputation of ACR component scores and PASI scores for the ACR and PASI response variables, respectively. Subjects with missing data or who have prematurely finished the study will be treated as missing.

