### 2.2.2.3 Other efficacy variables

The other efficacy variables are listed below and will be evaluated at scheduled visits in accordance with the schedule of study assessments in [Table 2-1](#):

- ACR20, ACR50, and ACR70 response at each visit (PA0009 EV, Week 12, 24, 36, 48, 60, 72, 84, 96, 100, 104), relative to PA0008 Baseline.
  - ACR20, ACR50 and ACR70 response will also be reported at each post-PA0008 Baseline visit in PA0008 through to PA0009 Week 104 (PA0008 Week 2, 4, 8, 12, 16, 20, 24, 36 and PA0009 EV [PA0008 Week 48], Week 12, 24, 36, 48, 60, 72, 84, 96, 100, 104), for subjects who were responders at PA0008 Week 12. These are additional variables to those specified in the protocol and will be used to assess maintenance of response.
- PASI75, PASI90 and PASI100 response at each visit (PA0009 EV, Week 12, 24, 36, 48, 60, 72, 84, 96, 100, 104), relative to PA0008 Baseline.
  - PASI75, PASI90 and PASI100 response will also be reported at each post-PA0008 Baseline visit in PA0008 through to PA0009 Week 104 (PA0008 Week 2, 4, 8, 12, 24 and 36 and PA0009 EV [PA0008 Week 48], Week 12, 24, 36, 48, 60, 72, 84, 96, 100, 104), for subjects who were responders at PA0008 Week 12. These are additional variables to those specified in the protocol and will be used to assess maintenance of response.
  - BSA at each visit in PA0009 will also be reported. This is additional to the protocol and was added as an additional method of assessing response in order to provide information at visits where the PASI data may be missing.
- Minimal Disease Activity (MDA) at each visit (PA0009 EV, Week 12, 24, 36, 48, 72, 96, 104).
- Change from Baseline of PA0008 value in Disease Activity Score-28 based on C-reactive protein (DAS28[CRP]) at each visit (PA0009 EV, Week 12, 24, 36, 48, 60, 72, 84, 96, 100, 104).
- Change from Baseline of PA0008 in MASES at each visit (PA0009 EV, Week 12, 24, 36, 48, 72, 96, 104).
- Change from Baseline of PA0008 in the LDI at each visit (PA0009 EV, Week 12, 24, 36, 48, 60, 72, 84, 96, 100, 104).
- Change from Baseline of PA0008 in Psoriatic Arthritis Impact of Disease-9 (PsAID-9) at each visit (PA0009 EV, Week 12, 24, 36, 48, 60, 72, 84, 96, 100, 104).
- Change from Baseline of PA0008 in Short Form 36-item Health Survey (SF-36) at each visit (PA0009 EV, Week 12, 24, 36, 48, 60, 72, 84, 96, 100, 104).

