Descriptive statistics will be displayed to provide an overview of the study results. For categorical variables, the number and percentage of subjects in each category will be presented. The denominator for percentages will be based on the number of subjects included in the respective analysis set. For observed case (OC) summaries, or summaries of data where no imputation is made for missing data, subjects with missing data will be accounted for by including a “Missing” category (corresponding to subjects with missing data for the variable being summarized) as the last row in the list of categories being summarized. Percentages will be presented to 1 decimal place. If the percentage is 100%, no decimal will be presented. If the percentage is 0, no percentage will be presented. The % sign will be presented in the column header, but not with each individual value.

For continuous variables, descriptive statistics will include number of subjects with available measurements (n), mean, standard deviation (SD), median, minimum, and maximum. Decimal places for descriptive statistics will apply the following rules:

- “n” will be an integer.
- Arithmetic and geometric mean, SD, and median will use 1 additional decimal place compared to the original data.

- Coefficient of variation (CV [%]) will be presented with 1 decimal place.
- Minimum and maximum will have the same number of decimal places as the original value.

The number of decimal places used for derived efficacy variables is shown in [Table 3-1](#).

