### 4.2 Handling of missing data

#### 4.2.1 Handling of missing data for efficacy analysis

Calculation of derived efficacy variables in the presence of missing data is described in individual subsections of [Section 8.1](#). All derived efficacy variables will be calculated using observed data, and any resulting missing data will be handled as described in this section. All nonresponder imputation (NRI) and MI imputation as described below will be performed only for subjects in the FAS for PA0009.

Additional methods for deriving the PASI response in the presence of missing data are described in [Section 4.2.2](#).

For assessments missing during PA0008, which were to be used in PA0009 for reporting maintenance of response, the following approach will be used:

- For summaries of binary data following NRI, the imputed value from the PA0008 database will be used.
- For summaries of non-imputed (OC) data, the assessment will be left as missing.

For all visits in PA0009 (including PA0009 EV), missing values for binary secondary/other efficacy variables (ACR20, ACR50, ACR70, PASI75, PASI90, PASI100, MDA) or values, which cannot be constructed (eg, for ACR either tender joint count [TJC]/swollen joint count [SJC] are missing or >2 out of the 5 remaining core set measures are missing) will be imputed using NRI. For each visit, subjects with missing data or who have dropped out of the study will be counted as nonresponders. This includes any subjects with missing Baseline values. For PASI response, NRI will be implemented only for subjects with BSA  $\geq 3\%$  at PA0008 Baseline.

For missing continuous secondary/other efficacy variables an MI approach will be used. This will be performed for the following endpoints:

- TJC and SJC

- Psoriasis Area and Severity Index (PASI)
  - For PASI the MI model will be restricted to subjects with a BSA affected by psoriasis of  $\geq 3\%$  at PA0008 Baseline. Subjects with a BSA affected by psoriasis of  $< 3\%$  at PA0008 Baseline will be excluded prior to performing the procedure outlined below.
- Patient's Global Assessment of Disease Activity (PGADA)
- Physician's Global Assessment of Disease Activity (PhGADA)
- Patient's Assessments of Arthritis Pain (PtAAP)
- Health Assessment Questionnaire – Disability Index (HAQ-DI)
- CRP

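### Dosed subjects with no efficacy value after the Entry Visit fall outside the FAS, so NRI never counts them as nonresponders and post-entry response rates can only stay the same or rise

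*SAP*

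**What the plan says.** SAP 3.6.3 requires, besides consent and at least one PA0009 dose, that the subject "have a valid measurement for at least 1 efficacy variable after PA0009 EV". Protocol 13.1 agrees: subjects must "have a valid measurement for at least 1 efficacy variable after PA0009 entry visit".

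The set then governs the efficacy tables:

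- SAP 3.6.3: "Secondary and other efficacy variables will be summarized for the FAS".
- SAP 3.1: "The denominator for percentages will be based on the number of subjects included in the respective analysis set".
- SAP 4.2.1: all NRI and MI "will be performed only for subjects in the FAS for PA0009".

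The NRI rule itself is stated without that limit. Protocol 13.8 says "each subject with missing data or who has prematurely finished the study will be counted as a nonresponder", and SAP 4.2.1 says that at each visit "subjects with missing data or who have dropped out of the study will be counted as nonresponders".

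The schedule puts the first post-entry efficacy assessments at Week 12. SAP 2.2.2.3 lists "ACR20, ACR50, and ACR70 response at each visit (PA0009 EV, Week 12, 24, 36" and later visits. Protocol 8.2 has no efficacy assessment at Weeks 4 and 8.

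**The concern.** NRI is meant to charge early loss against the response rate. Here the earliest losses can escape the charge, because membership of the FAS depends on what happens after dosing. Take two subjects who stop at Week 6. The one who attends the Early Termination visit supplies efficacy data, enters the FAS and is a nonresponder at Week 48. The one who does not return supplies nothing and disappears from numerator and denominator alike.

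At stake are the post-entry NRI rates: the secondary ACR20/50/70 and PASI75/90 responses at Week 48, and the by-visit ACR, PASI and MDA rates. The Week 48 subgroup summaries and the post-entry rows of the maintenance-of-response tables are also affected. The observed-case and MI versions use the FAS too, so no planned analysis brings these subjects back.

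**Working it through.** The plan has no sample size, power or alpha figure to reproduce. The check has two parts: a trace of the rules, then the size of the effect.

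**Who is affected**

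1. In the Safety Set: one PA0009 dose is enough (SAP 3.6.2).
2. Weeks 4 and 8 supply no scheduled efficacy value (Protocol 8.2), so the first scheduled one is Week 12.
3. A subject who leaves before Week 12 but attends the Early Termination visit has the full Week 104 efficacy set (Protocol 8.8 and 8.10) and stays in the FAS.
4. CRP is drawn at the Safety Follow-up visit (Protocol 8.9), and SAP 8.3 lists CRP among the efficacy variables. A subject with only that value arguably qualifies; SAP 3.6.3 does not settle it.
5. What remains is a dosed subject with none of these. That subject is outside the FAS, outside the denominator and outside NRI.

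**Direction**

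- Post-entry visits: the excluded subjects have no data there, so NRI would make each a nonresponder. Removing nonresponders leaves the rate unchanged (if none are removed or the rate is zero) or raises it.
- Entry Visit and PA0008 visits in the maintenance tables: the excluded subjects may have observed responses, so the direction is unknown.
- Continuous endpoints: MI is also limited to the FAS, and the direction there cannot be told from the documents.

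**Size at a post-entry visit**

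Let N be the number dosed, k the number with no post-entry efficacy value and r the number of responders.

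- FAS rate = r/(N − k)
- All-dosed rate = r/N = FAS rate × (N − k)/N
- Overstatement = FAS rate × k/N

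Inputs: N = 200 is the ceiling in Protocol 13.10 and SAP 2.4. The 65% FAS rate and k are assumptions.

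| k | All-dosed rate, 65% × (200 − k)/200 | Overstatement (points) |
|---|---|---|
| 0 | 65.00% | 0 |
| 2 | 64.35% | 0.65 |
| 4 | 63.70% | 1.30 |
| 6 | 63.05% | 1.95 |
| 10 | 61.75% | 3.25 |

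Starting instead from an assumed all-dosed rate, with r fixed:

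| All-dosed rate | FAS rate, k = 2 | FAS rate, k = 10 |
|---|---|---|
| 60/200 = 30.0% | 60/198 = 30.3% | 60/190 = 31.6% |
| 100/200 = 50.0% | 100/198 = 50.5% | 100/190 = 52.6% |
| 140/200 = 70.0% | 140/198 = 70.7% | 140/190 = 73.7% |

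Small cells move more. The maintenance tables split Week 12 responders of PA0008 over seven treatment sequences (SAP 3.7 and 8.3.1). In an assumed cell of 20 with 14 responders at a post-entry visit, losing one nonresponder changes 14/20 = 70.0% to 14/19 = 73.7%.

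**The case against.** The strongest reply is that this is a consistent design choice. The protocol defines this FAS, summarizes efficacy on it (13.4) and applies NRI (13.8); read together, NRI works inside the set the protocol chose. The SAP follows that and says so openly. This stands as far as it goes: a reader might infer that the SAP departs from the protocol or that NRI is defeated outright, and neither is right. It does not remove the tension inside both documents, where premature leavers are said to count as nonresponders and some do not.

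The affected group may also be very small, or empty. Withdrawn subjects are asked to complete the Early Termination and Safety Follow-up visits (Protocol 6.3), and one valid value of one efficacy variable suffices. Entrants completed PA0008 without meeting withdrawal criteria and were judged reliable (Protocol 6.1). This stands, and it is why k = 0 belongs in the range. But the protocol also provides for loss to follow-up (6.3), so the group cannot be assumed empty.

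Finally, the effect will be visible: SAP 5.1 tabulates the size of each analysis set and lists every exclusion with its reason. That shows k but does not correct the rates.

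**Conclusion.** The point holds for dosed subjects with no efficacy value at all after the Entry Visit. For them the FAS condition overrides the stated NRI rule, and at post-entry visits the effect on NRI response rates is nil or upward.

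A reader might infer that everyone who leaves before Week 12 drops out of the denominator. The documents do not support that: Early Termination attenders stay in the FAS and count as nonresponders at Week 48. Nor can one say that every reported ACR and PASI rate is pushed up, because Entry Visit and PA0008 rows can move either way.

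With 200 dosed and a 65% FAS rate, both assumed, the overstatement is 0 to 3.25 points for k from 0 to 10. The documents give neither k nor the response rate. The study is single-arm and descriptive, so no test, error rate or power is involved, and the primary safety analysis does not use the FAS. The consequence is modest, but the bias has one direction at the visits that matter and is cheap to remove.

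**What to change.** For NRI responder summaries (ACR, PASI, MDA) at post-entry visits, use all dosed PA0009 subjects, that is the Safety Set, as denominator. For PASI, restrict this to subjects with BSA of at least 3% at PA0008 Baseline. Apply any further restriction a table already carries, such as PA0008 Week 12 response in the maintenance tables. Count subjects with no post-entry efficacy data as nonresponders at those visits.

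Three details need care:

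- Keep the SAP 4.2.1 rule that subjects with missing Baseline values are nonresponders. Requiring a PA0008 Baseline value for ACR would create a new exclusion of the same kind.
- Keep observed responses at the Entry Visit and PA0008 visits; they must not be overwritten as nonresponse.
- Retain the current FAS result as supportive.

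If the main denominator is to stay as it is, add the Safety Set version as a sensitivity analysis at minimum. Because the FAS is also defined in the protocol, record the change in SAP 3.10.

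The cost is a short SAP edit, the SAP 3.10 entry and a rerun of the response tables. If k is above zero, the rates become slightly less favourable.

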### **3.7 Treatment assignment and treatment groups**

This is an open label, single arm study.

Treatment group at the completion of PA0008 (presented as ‘BKZ 160mg’ or ‘BKZ 320mg’) and an overall ‘BKZ Total’ column will be used to summarize data in PA0009.

The endpoints assessing maintenance of ACR and PASI response over time will be summarized by treatment sequence across PA0008 and PA0009. Treatment sequences take the form ‘A/B/C’, where A is the treatment in the first 12 weeks of PA0008, B is the treatment from Week 12 to Week 48 of PA0008, and C is the treatment in PA0009. The seven planned treatment sequences are as follows:

- Placebo/BKZ 160mg/BKZ 160mg.
- Placebo/BKZ 320mg/BKZ 160mg.
- BKZ 16mg/BKZ 160mg/BKZ 160mg.
- BKZ 16mg/BKZ 320mg/BKZ 160mg.
- BKZ 160mg loading dose (LD)/BKZ 160mg/BKZ 160mg.
- BKZ 160mg/BKZ 160mg/BKZ 160mg.
- BKZ 320mg/BKZ 320mg/BKZ 160mg.

For safety summaries the following will be presented:

- Safety summaries including PA0009 data only will be presented by treatment group at the completion of PA0008 and overall.
- Safety summaries including data from both PA0008 and PA0009 combined will be presented for 'BKZ 160mg', 'BKZ 320mg', and 'BKZ Total'. The assignment of each of the sequences to the columns in this table is presented in [Table 3-2](#).
  - The 'BKZ 160mg' treatment column in these tables will include subjects in both the BKZ 160mgLD and BKZ 160mg treatment groups.
  - For each column, only those periods for which the specified treatment is received will contribute to the summary ie, for sequence BKZ 16mg/BKZ 320mg/BKZ 160mg, the 16mg period will contribute to the BKZ Total column only, the BKZ 320mg period will contribute to the BKZ 320mg column and the BKZ Total column only, and the BKZ 160mg period will contribute to the BKZ 160mg column and the BKZ Total column only.

**Table 3-2: Treatment sequence assignment for safety summaries**

Sequence	BKZ 160mg	BKZ 320mg	BKZ Total
Placebo/BKZ 160mg/BKZ 160mg	X		X
Placebo/BKZ 320mg/BKZ 160mg	X	X	X
BKZ 16mg/BKZ 160mg/BKZ 160mg	X		X
BKZ 16mg/BKZ 320mg/BKZ 160mg	X	X	X
BKZ 160mg LD/BKZ 160mg/BKZ 160mg	X		X
BKZ 160mg/BKZ 160mg/BKZ 160mg	X		X
BKZ 320mg/BKZ 320mg/BKZ 160mg	X	X	X

BKZ=bimekizumab; LD=loading dose.

- For all safety summaries, subjects who took bimekizumab 320mg during PA0008 will contribute to all 3 columns. Subjects who did not take 320mg in PA0008 will contribute to the ‘BKZ 160mg’ and ‘BKZ Total’ columns.
- The combined summaries will include all data from PA0008 in addition to PA0009 only for subjects who were enrolled in PA0009.
- The PA0009 only summaries will include only data collected in PA0009 (unless otherwise stated).

Subjects will be summarized based on the actual/received treatment or the planned treatment for different analysis sets as follows:

- ES: planned treatment.
- SS and SS Sub-populations: actual treatment.
- FAS: planned treatment.

For actual and planned treatments in PA0008, the data will be used directly from the PA0008 analysis database without any rederivation of treatment assignments in each period.

In PA0009 it will be assumed that all subjects received the correct treatment as the dose level of bimekizumab is the same for all subjects and throughout the study (160mg). If a subject missed a dose at PA0008 Week 48, they will also be considered to have received the planned treatment. Thus for all subjects in PA0009, the actual treatment will be the same as the planned treatment.

### 3.8 Center pooling strategy

Centers at PA0008 Baseline will be grouped into the geographic regions of North America (county code USA) and Europe (country codes CZE, DEU, HUN, POL, RUS) for use as a

covariate in statistical analyses and for subgroup analyses (see [Section 4.1](#) and [Section 8.4](#)). An additional region grouping of North America (country code USA), Eastern Europe (country codes CZE, HUN, POL, RUS) and Western Europe (country code DEU) will be derived in the datasets for possible use in future integration.

### 3.9 Coding dictionaries

Medical history and AEs will be coded using the Medical Dictionary for Regulatory Activities (MedDRA) version 19.0. Medical history conditions will be classified by primary system organ class (SOC) and preferred term (PT). AEs will be classified by primary system organ class (SOC), high level term (HLT) and preferred term (PT).

Prior and concomitant medications will be coded using version SEP2015 of the World Health Organization Drug Dictionary and will be classified by Anatomical Main Group, Pharmacological Subgroup, and PT.

Medical procedures will not be coded.

### 3.10 Changes to protocol-defined analyses

The following changes have been made to the protocol-defined analyses:

- Summaries of ACR20, ACR50, ACR70, PASI75, PASI90, and PASI100 response at each post-PA0008 Baseline visit have been added for subjects who were responders at PA0008 Week 12. These summaries include all post-Baseline PA0008 visits through to PA0009 Week 104 and will be used to assess maintenance of response.
- Summaries of BSA at each visit in PA0009 have been added as an additional method of assessing response in order to provide information at visits where the PASI data may be missing.
- Summaries by randomized treatment in PA0008 will not be produced, as subjects will have been on a constant dose of bimekizumab 160mg or 320mg for at least 36 weeks prior to PA0009 entry. Maintenance of response displays will be split by treatment sequence across PA0008 and PA0009. Safety displays using PA0008 information will incorporate exposure in PA0008.
- The protocol stated that all safety analyses would be performed for both SS Sub-populations; instead only key safety analyses will be repeated by SS Sub-population as identified in [Section 10](#). These analyses will be performed only in the event that the number of subjects receiving rescue medication is  $\geq 10\%$  of the total number of subjects in the SS.
- The protocol stated that figures presenting the relationship between ACR20 response and ADAb positivity over time would be produced. This has been changed to use the ACR50 response instead as this is considered to be the key efficacy endpoint with respect to ACR.

#### 3.10.1 Changes related to COVID-19

The impact of the COVID-19 pandemic on study procedures/conduct and on the primary safety endpoints (TEAEs, serious TEAEs, and study withdrawal due to TEAEs) will be investigated and additional outputs provided as appropriate. These analyses were not planned as part of the protocol as the pandemic was not ongoing at the time of protocol finalization.

The additional analyses are described in the following sections of the SAP:

- Subject disposition, including details of impacted visits and effects on collection and reporting of efficacy data ([Section 5.1.1](#))
- Adverse events ([Section 10.2.4](#))

## 4 STATISTICAL/ANALYTICAL ISSUES

### 4.1 Adjustments for covariates

All multiple imputation (MI) models (see [Section 4.2.1](#)) will include the following covariates:

- Geographic region at PA0008 Baseline (North America, Europe), as defined in [Section 3.8](#).
- Previous (past) tumor necrosis factor (TNF) inhibitor agent exposure in PA0008. The value in the PA0008 database for past anti-TNF therapy (as collected on the eCRF) will be used for PA0009, without additional derivation.

Missing efficacy data will be handled as described in [Section 4.2.1](#). No imputation will be made for missing safety or background data, except as described in [Section 4.2.3](#) and [Section 4.2.4](#).

